Prednisolone ¹⁷			X	X	X	Х	X	X	X	X	Х	X	X	X, taper	X, taper			
Trimethoprim/sulfamethoxa zole 18			X	X	X	Х	X	X	X	X	Х	Х	X	X	X	х	Х	
Lansoprazole 19			X	X	X	X	X	X	X	X	X	X	X	X				
IVIG administration 20						AN				AN	AN	AN	AN	AN			AN	
Bilat Intrathalamic Infusion					X													
Intrathecal Infusion						X												
LP CSF collection 21	X					X								X			X	X^{23}
CSF HexA activity level, GM2 ganglioside	X					Х								X			X	X ²³
Adverse Events review		X	X	X	X	X	X	X	X	X	X	X	X	X	X	X	X	X
Concomitant medication review		X	X	X	X	X	X	X	X	X	X	X	X	X	X	X	X	X

Footnotes:

Page 61 of 97

^{*} Enrollment of Participants will be done at staggered 4-week intervals, based on satisfactory DSMC and Sponsor review of 4-week safety data. The screening activities marked with an asterisk may be performed prior to DSMC data review conclusion of prior participants. All other assessments must not be performed prior to DSMC/Sponsor review and approval to enroll the next participant.

^{*} Blue Indicates this occurs at Massachusetts General Hospital, Red indicates it occurs at UMass Chan Medical School

Clinical Study Protocol: AXO-GM2-001

Version 8.0, 09 June 2023

- 1. Verification of *HEXA* or *HEXB* gene mutation and modifiers by reports
- 2. 1hr or 24hr EEG at the discretion of the clinician based on the status of the participants
- 3. Echocardiogram report within 3 months of screening is acceptable.
- 4. To be used by neurosurgeon for thalamic target navigation planning. Scan should include brain and spinal cord. Scan may be obtained up to 14 days prior to surgery to allow for adequate time for planning and preparation.
- 5. To be reviewed by study neurosurgeon as part of surgical readiness determination.
- 6. Safety labs will be prioritized based on the participant's condition at the discretion of the investigator. Additional safety labs may be required for participant management. Safety labs include the following: CBC with auto-differential and comprehensive metabolic panel, AST, ALT, ALP repeated as needed if 2X baseline, ELISpot. A CH50 may also be performed as clinically indicated, i.e., platelet count decrease. Additionally, PT, PTT, and INR will be assessed prior to surgery.
- 7. Will be assessed as needed after Day -2
- 8. IgG levels to be done at least 3 days prior to the scheduled visit, at a local lab as necessary. Performed as needed at month 6, contingent on results from month 3
- 9. Blood will be collected for research as tolerated by the participant and will be frozen for later use or used for the isolation of serum or PBMCs. The amount of research blood collected, and its intended use, will vary between visits based on the overall volume of blood collected within a 1-week period remaining < 10 mL. Sample prioritization will be determined by investigator and Sponsor if collected blood volume is limited. Collect blood on Visit B (Day -16) prior to immunosuppression.. Blood collected for research can include anti-AAVrh8 antibodies (ADA), transgene antibodies (ADA) and neutralizing antibodies (Nabs) if needed. The priority should be the antibodies followed by the serum HEXA activity and then GM2 ganglioside levels in serum.
- 10. Infectious disease testing will be performed as clinically indicated (i.e., based on Medical History) and will include HIV, hepatitis A, B and C, herpes simplex virus, cytomegalovirus, Epstein Barr virus, varicella zoster virus, and toxoplasmosis
- 11. Measurements include systolic and diastolic blood pressure, pulse rate per minute, respiratory rate per minute, and temperature
- 12. Comprehensive exam or limited exam at the discretion of the clinician based on participant's status. Exams may be videotaped. For Visit 1b (Day 2), perform neurologic checks every 2h for the first 24h, and full physical and neurological exam 24h, 48h, and 72h post infusion while inpatient.
- 13. Caregivers will have option to have central venous catheter inserted into participants prior to surgical gene transfer to ensure venous access and reduce difficulty and pain associate with blood draws during the study
- 14. Rituximab IV infusion at 375 mg/m² body surface area (BSA). As needed at Day -2 for persistent CD20 count greater than or equal to 5%
- 15. Solu-Medrol IV infusion at 10 mg/kg
- 16. Sirolimus oral at 1.5 mg/m² BSA; Adjust dose to achieve serum trough levels of 7-12 ng/mL as needed. To be weaned starting Visit 12/Week 24 according to the following regimen: Week 24-25: reduce dose by 50%; Week 25-26: reduce Week 24-25 dose by 50%; Week 26-27: reduce Week 25-26 dose by 50% then stop
- 17. Prednisolone 1-2 mg/kg/day, to be tapered starting Visit 9/Week 12 according to the following regimen: Week 12-13: reduce dose by 50%; Week 13-14: reduce week 12-13 dose by 50%; Week 14-15: reduce week 13-14 dose by 50%; Week 15-16: reduce week 13-14 dose by 50% then stop.
- 18. The dose of trimethoprim/sulfamethoxazole 2.5 mg/kg/day BID on 2 consecutive days per week (PO or by feeding tube) or per PI discretion, to be discontinued following completion of sirolimus wean.
- 19. Lansoprazole suspension of 1 to 1.5 mg/kg/day PO, to be discontinued following completion of prednisolone tapering.
- 20. IVIG administration 1 gm/kg (1000 mg/kg) if IgG levels < 500 mL/dL. Dose adjusted to maintain serum trough levels of 500-1000 mg/dL after vector infusion. On Day 1, IVIG administration will occur later in the day, after treatment infusion has completed.
- 21. Divided between clinical and research analyses. Visit 1b (Day -2) CSF collection should be pre-administration.
- 22. Participants must have a swallow evaluation test performed within 6 months prior to AXO-AAV-GM2 administration to assess risk of aspiration. If aspiration risk is identified, it must be clinically managed prior to surgical procedures. Participants must have a swallow evaluation test performed at baseline and a clinical assessment of swallowing and a swallow study, if warranted, at Visit 9 (Week 12), Visit 12 (Week 24), Visit 13 (Week 48), and yearly thereafter for Years 2-5 (see Table 17).
- 23. May be completed if visit occurs in person however not if the visit is completed as a tele-health
- 24. Tele-health will occur if Pt does not come to site in person

AN - As Needed

Confidential Page 62 of 97

Clinical Study Protocol: AXO-GM2-001

Version 8.0, 09 June 2023

 Table 16:
 Schedule of Juvenile-Onset Participant LTFU

Schedule of Activities	Visit 16	Visit 17	Visit 18	Visit 19	Visit 20
	Week 120	Week 144	Week 168	Week 192	Week 240
	±28d	±28d	±28d	±28d	±28d
Vital Signs	X^1	X^1	X ¹	X^1	X^1
Weight	X ¹	X ¹	X ¹	X^1	X^1
Height	X^1	X^1	X ¹	X^1	X^1
Physical Examination	X ¹	X ¹	X ¹	X^1	X^1
Neurologic Examination (may be videotaped)	X ¹	X ¹	X ¹	X^1	X^1
Tele-health follow-up	X^2	X^2	X^2	X^2	X^2
Participant Appropriate Neuro-Cognitive Assessments		X ¹		X^1	X^1
Clinical Global Impression		X ¹		X^1	X^1
Motor Assessments		X ¹		X^1	X^1
BAER/VER/SSEP		X^1			
MRI, MRS, DTI		X^1		X^1	X^1
CBC with auto-differential	X^1	X ¹	X ¹	X^1	X^1
Comprehensive metabolic profile	X ¹	X ¹	X ¹	X^1	X^1
CH50 – AN due to platelet count decrease	AN	AN	AN	AN	AN
CSF HexA activity level, GM2 ganglioside		X ¹		X^1	X^1
CD 19, 20 count	AN	AN	AN	AN	AN
IgG levels	AN	AN	AN	AN	AN
Research blood collection	X ¹				
Anti-AAVrh8 antibodies (ADA)	X^1	X^1	X ¹	X^1	X^1
Transgene antibodies (ADA)	X ¹				
Neutralizing antibodies (Nabs)	X ¹				
Serum HexA activity levels	X ¹	X ¹	X ¹	X^1	X ¹
Serum GM2 ganglioside levels	X ¹	X ¹	X ¹	X^1	X^1
ELISpot	X ¹	X ¹	X ¹	X^1	X ¹
Swallow Study		X ¹		X^1	X ¹
Adverse Events review	X	X	X	X	X

Confidential Page 63 of 97

AXO-AAV-GM2

UMass Chan Medical School

Clinical Study Protocol: AXO-GM2-001

Version 8.0, 09 June 2023

 Table 16:
 Schedule of Juvenile-Onset Participant LTFU (Continued)

Schedule of Activities	Visit 16	Visit 17	Visit 18	Visit 19	Visit 20
	Week 120	Week 144	Week 168	Week 192	Week 240
	±28d	±28d	±28d	±28d	±28d
Concomitant medication review	X	X	X	X	X
Urinalysis		AN		AN	AN

AN – As Needed

Confidential Page 64 of 97

^{1.} May be completed if visit occurs in person however not if the visit is completed as a tele-health

^{2.} Tele-health will occur if Pt does not come to site in person

UMass Chan Medical School Clinical Study Protocol: AXO-GM2-001

Version 8.0, 09 June 2023

 Table 17:
 Schedule of Infantile-Onset Participant LTFU

Schedule of Activities	Visit 14	Visit 15	Visit 16	Visit 17	Visit 18	Visit 19	Visit 20
	Week 72	Week 96	Week 120	Week 144	Week 168	Week 192	Week 240
	±28d	±28d	±28d	±28d	±28d	±28d	±28d
Vital Signs	X ¹	X^1	X ¹	X^1	X ¹	X^1	X^1
Weight	X ¹	X ¹	X ¹	X^1	X ¹	X ¹	X ¹
Height	X ¹	X ¹	X ¹	X^1	X^1	X ¹	X ¹
Physical Examination	X ¹	X ¹	X ¹	X^1	X ¹	X ¹	X ¹
Neurologic Examination	X ¹	X ¹	X ¹	X^1	X ¹	X ¹	X ¹
Tele-health Follow-up	X ²	X^2	X^2	X^2	X^2	X^2	X^2
HINE-2	X ¹	X ¹	X ¹	X^1	X ¹	X ¹	X ¹
BSID-III	X ¹	X^1	X^1	X^1	X ¹	X^1	X^1
Vineland 3	X ¹	X ¹	X ¹	X^1	X ¹	X ¹	X ¹
MRI, MRS, DTI		X ¹		X^1			X ¹
BAER/VER/SSEP				X^1			
Clinical Global Impression	X ¹	X^1	X^1	X^1	X ¹	X^1	X^1
CBC with auto-differential	X ¹	X ¹	X ¹	X^1	X ¹	X ¹	X ¹
Comprehensive metabolic panel	X ¹	X ¹	X ¹	X^1	X ¹	X ¹	X ¹
CH50 – AN due to platelet count decrease	X ¹	X^1	X^1	X^1	X ¹	X^1	X^1
CSF HexA activity level, GM2 ganglioside		X ¹		X^1		X ¹	X^1
CD 19, 20 count	AN	AN	AN	AN	AN	AN	AN
IgG levels	X ¹	X^1	X^1	X^1	X^1	X^1	X^1

Page 65 of 97

Clinical Study Protocol: AXO-GM2-001

Version 8.0, 09 June 2023

 Table 17:
 Schedule of Infantile-Onset Participant LTFU (Continued)

Schedule of Activities	Visit 14	Visit 15	Visit 16	Visit 17	Visit 18	Visit 19	Visit 20
	Week 72	Week 96	Week 120	Week 144	Week 168	Week 192	Week 240
	±28d						
Research blood collection	X ¹	X^1	X^1	X ¹	X^1	X^1	X^1
Anti-AAVrh8 antibodies (ADA)	X ¹	X^1	X^1	X ¹	X^1	X^1	X^1
Transgene antibodies (ADA)	X^1	X^1	X ¹	X^1	X ¹	X^1	X^1
Neutralizing antibodies (Nabs)	X ¹						
Serum HexA activity level	X ¹	X^1	X^1	X ¹	X^1	X^1	X^1
Serum GM2 ganglioside level	X ¹	X^1	X ¹	X ¹	X ¹	X ¹	X^1
ELISpot	X ¹						
Swallow Study		X^1		X^1		X ¹	X^1
Adverse Events review	X	X	X	X	X	X	X
Concomitant medication review	X	X	X	X	X	X	X
Urinalysis	AN	AN	-	AN	-	AN	AN

AN – As Needed.

Page 66 of 97

^{1.} May be completed if visit occurs in person however not if the visit is completed as a tele-health

^{2.} Tele-health will occur if Pt does not come to site in person

Version 8.0, 09 June 2023

9. SELECTION AND WITHDRAWAL OF PARTICIPANTS

In order to reduce participant burden and aid in the participant selection process, screening may be initiated by a virtual visit with the study staff prior to traveling to the study site. During the virtual visit, study staff will conduct a preliminary assessment of participant eligibility. The parent(s)/caregiver(s) will be asked about the participant's medical history and may be asked to help in demonstrating the participant's functional ability. This virtual visit may be video recorded.

9.1. Participant Inclusion Criteria

- 1. Male or female participants with genetically diagnosed TSD or SD mutations of either *HEXA* gene or *HEXB* gene
 - a. Stage 1 juvenile-onset participants must be \geq 2 years old and \leq 12 years old at time of gene transfer
 - ii. Diagnosis consistent with juvenile-onset TSD or SD
 - c. Stage 1 infantile-onset participants must be between ≥ 6 months and ≤ 20 months of age at the time of gene transfer
 - i. Diagnosis consistent with infantile-onset TSD or SD
- 2. Juvenile onset participants must demonstrate a minimum of 2 of the following age-appropriate clinical features/abilities, confirmed by the site examiner at the time of screening and reaffirmed prior to the initiation of immunosuppression:
 - a. A Gross Motor Function Classification-MLD (GMFC-MLD) score of 0, 1 or 2. The minimum gross motor function (GMFC-MLD level 2) is the 'ability to walk with support and walking without support is not possible (fewer than 5 steps)'. (Participants aged 2-12 years) Note: Any form of support is permitted; however, the participant must initiate each step and complete it for a total of 5 steps.
 - b. Fine Motor Function
 - For Participants aged 4-12 years: A Manual Ability Classification System (MACS) score of I, II, III, or IV. The minimum level of manual ability (level IV) corresponds to 'Handles a limited selection of easily managed objects in adapted situations'.
 - For participants aged 2-4 years: attainment of fine motor function/coordination abilities and milestones with normal or a reduced quality of performance. That is, the ability to coordinate fingers and both hands to play, such as swinging a bat or opening a container (pathways.org) OR the ability to use fingertips to pick up small objects, i.e., the child uses pad of his/her thumb and any fingertip to grasp a pellet or small object as described in BSID III Fine Motor Sub-test Item #26.
 - c. Speech:
 - For participants aged 4-12 years, a speech disturbance score of 0, 1, 2 or 3 on the speech disturbance subset of the Scale for Assessment and Rating of Ataxia

Confidential Page 67 of 97

UMass Chan Medical School Clinical Study Protocol: AXO-GM2-001

Version 8.0, 09 June 2023

(SARA). The minimum speech requirement is a speech disturbance in which most words can be understood, with occasional words difficult to understand secondary to dysarthria.

- Participants aged 2-4 years who have attained the communication milestone of ability to consistently use 2-3 word phrases may be assessed in line with this criterion using the speech disturbance subset of the SARA.
- For participants aged 2-4 years who have not yet attained the above communication milestone, the minimum requirement is the ability to imitate at least one word, even if the imitation consists of vowels only (BSID III, expressive communication subtest, item #16)
- 3. Infantile onset participants must demonstrate current* or historical† ability to sit without support for at least 5 seconds
 - * As assessed in item 22 of the BSID-III Gross Motor Scale or documented medical records
 - † Documented within available medical records

In addition, infantile onset participants must demonstrate a **minimum of 3** of the following developmental skills confirmed by the site examiner at the time of screening and reaffirmed prior to the initiation of immunosuppression:

- a. Head control While supine, with head in midline turns head symmetrically (score of 3 on GMFM item 1)
- b. Uses hands to support self while sitting
- c. Reach for an object that is held out for them above their chest while supine
- d. Transfer of object from hand to hand while supine
- e. Eye tracking while supine
- f. Looks at an object of interest for at least 3 continuous seconds
- 4. Surgical readiness for gene transfer route of administration confirmed by the study neurosurgeon, based on examination and MRI findings

The following findings will disallow the performance of the BiTh procedure, thereby excluding the participant from participation:

- Any scalp and skull related lesion (e.g. vascular, infectious) over the surgical entry area
- Any intracranial lesion (e.g. vascular, cystic, other mass lesions), significant immaturity, or deformity of the brain anatomy that would make the intended surgical trajectory high risk

The following findings will disallow the performance of the ICM/IT procedure, thereby excluding the participant from participation:

- Any skin related lesion (e.g. vascular, infectious) over the lumbar puncture site
- Any intraspinal or intracranial lesion in posterior fossa (e.g. vascular, cystic, other mass lesions) or significantly deformed, distorted brain, spinal and cisternal anatomy that make the intended intrathecal trajectory high risk or not feasible

Confidential Page 68 of 97

Clinical Study Protocol: AXO-GM2-001

Version 8.0, 09 June 2023

Participants otherwise eligible for study participation but deemed not currently fit for neurosurgery may be re-screened at the discretion of the investigator

- 5. Participants receiving off-label miglustat and/or Tanganil must be willing to discontinue these therapies 30 days prior to the start of screening
- 6. Ability to reliably travel to the study sites for study visits according to the Schedule of Assessments

9.2. Participant Exclusion Criteria

- 1. Presence of G269S or W474C mutation in HEXA
- 2. Evidence of lower respiratory tract aspiration not easily manageable with thickening of feedings or substitution of a modified bottle nipple, as judged on a multi-texture contrast swallow.
- 3. History of multiple aspiration pneumonias occurring in the past twelve months.
- 4. Respiratory support in the form of ventilation (invasive or non-invasive).
- 5. History of drug-resistant seizures or status epilepticus
- 6. History and/or findings of spinal cord disease that would preclude the LP and ICM/IT infusion procedures including:
 - Infectious process involving the spinal canal which may cause adhesions or septations in the spinal and/or subarachnoid space
 - Previous spinal surgeries
 - History of trauma, bleeding in the spinal canal
 - Vascular or cystic lesions, or any other mass lesion
 - Congenital deformities and malformations involving the spinal canal
 - Posterior fossa findings (low lying cerebellar tonsils, crowded foramen magnum, small or absent cisterna magna)
- 7. The participant's parent(s) or legal guardian(s) is unable to understand the nature, scope, and possible consequences of the study, or does not agree to comply with the protocol defined schedule of assessments
- 8. Any prior participation in a study in which a gene therapy vector or stem cell transplantation was administered
- 9. Immunizations of any kind in the month prior to screening
- 10. Cardiomyopathy or other cardiac disease (based on echocardiogram and/or ECG) that in the opinion of the Investigator would deem the participant unsafe to undergo surgical gene transfer
- 11. Indwelling ferromagnetic devices that would preclude MRI/ /MRS/DTI imaging
- 12. Ongoing medical condition that is deemed by the Investigator to interfere with the conduct or assessments of the study

Confidential Page 69 of 97

Clinical Study Protocol: AXO-GM2-001

Version 8.0, 09 June 2023

13. Current clinically significant infections including any requiring systemic treatment including but not limited to human immunodeficiency virus (HIV), Hepatitis A, B, or C

- 14. History of or current chemotherapy, radiotherapy or other immunosuppressive therapy within the past 30 days. corticosteroid treatment may be permitted at the discretion of the PI
- 15. Clinically significant laboratory abnormalities:

Based on age-specific reference range and determined by the investigator

- Total WBC count
- Hemoglobin
- Creatinine
- Pancreatic enzymes

Based on the following thresholds

- Platelet count ($< 150,000/\mu L$)
- Prothrombin (PT), partial thromboplastin time (PTT) >2X normal
- Liver transaminases (Hy's Law: > 3x elevations above the ULN of ALT or AST and serum total bilirubin > 2xULN)
- 16. Participants for whom any of the proposed study procedures or medications (i.e. sirolimus, trimethoprim/sulfamethoxazole) would be contraindicated
- 17. Failure to thrive, defined as falling 20 percentiles (20/100) in body weight in the 3 months preceding Screening/Baseline
- 18. Participant is not suitable for participation in the study in the opinion of the Principal Investigator

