8.2. Prophylactic Immune Tolerance Induction (ITI) Regimen

To prevent the risks of an inflammatory response and to protect AAV-transduced cells from immune response to the AAVrh8 capsid and/or transgene, participants will be immunosuppressed prior to administration of AXO-AAV-GM2 treatment. The ITI regimen will be maintained as described below.

Starting on Day -7 of the study, the following will be initiated:

- Rituximab* at 375 mg/m² BSA (IV infusion)
 - *Pre-medication for rituximab infusion will include:
 - acetaminophen 10-15 mg/kg given either PO, g-tube or rectal one time prior to infusion (may repeat q 4 hours for temperature >38.3°C)
 - diphenhydramine 1 mg/kg given either PO, g-tube or IV one time prior to infusion (may repeat 1 mg/kg IV PRN)
- Solu-Medrol at 10 mg/kg (IV infusion)
- Sirolimus* at 1.5 mg/m² BSA/day (PO or by feeding tube) *adjustment permitted to achieve trough levels of 7-12 ng/mL
- Prednisolone at 1-2 mg/kg/day (PO or by feeding tube)
- Lansoprazole at 1-1.5 mg/kg/day (PO or by feeding tube)
- Trimethoprim/sulfamethoxazole 2.5 mg/kg/day BID on 2 consecutive days per week (PO or by feeding tube) or per PI discretion

Day -2, Day 1 (BiTh Infusion Day), Day 2 (ICM/IT Infusion Day):

• Rituximab* at 375 mg/m² BSA (IV infusion), as needed for persistent CD20 count ≥ 5%

*Pre-medication for rituximab infusion will include:

- acetaminophen 10-15 mg/kg given either PO, g-tube or rectal one time prior to infusion (may repeat q 4 hours for temperature >38.3°C)
- diphenhydramine 1 mg/kg given either PO, g-tube or IV one time prior to infusion (may repeat 1 mg/kg IV PRN)
- Continuation of sirolimus*, prednisolone, and lansoprazole dosing (PO or by feeding tube)
 - *adjustment permitted to achieve trough levels of 7-12 ng/mL
- Continuation of trimethoprim/sulfamethoxazole 2.5 mg/kg/day BID on 2 consecutive days (PO or by feeding tube) or per PI discretion

Day 2-8:

- Continuation of sirolimus*, prednisolone, and lansoprazole dosing (PO or by feeding tube)
 - *adjustment permitted to achieve trough levels of 7-12 ng/mL
- Continuation of trimethoprim/sulfamethoxazole 2.5 mg/kg/day BID on 2 consecutive days per week (PO or by feeding tube) or per PI discretion

Confidential Page 40 of 97

Clinical Study Protocol: AXO-GM2-001

Version 8.0, 09 June 2023

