The ITI regimen will be stopped upon evidence of any of the following severe conditions for which no other cause has been identified: (1) intractable, severe opportunistic infections, not able to be managed with antibiotic, antifungal or antiviral therapy; (2) renal dysfunction (rising creatinine or BUN); (3) severe rash; (4) evidence of CNS problems including seizures or encephalopathy; (5) bleeding or clinically significant elevation of bleeding parameters.

Participants requiring discontinuation of the ITI regimen prior to Visit 1a (Day 1) will not be eligible for gene transfer and will be withdrawn from the study.

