8.3.2. Immune Tolerance Induction (ITI) Regimen Justification

The prophylactic ITI regimen will be administered starting 7 days prior to gene transfer and will continue to week 24 to prevent antibody response to AAV capsid in participants receiving gene therapy. The potential for immune modulation to prevent antibody response to AAV capsid in participants receiving gene therapy was demonstrated by Corti et. al following a trial of intra-diaphragmatic injection of AAV1-GAA in participants with infantile Pompe disease (Corti et al. 2017). Three CRIM negative participants receiving AAV1-hGAA had also received chronic immune modulation with rituximab and sirolimus due to pre-existing immune responses to enzyme replacement therapy (ERT). These participants had no immunologic response to AAV capsid proteins or the GAA protein. This was in contrast to the 5 CRIM positive participants who had not received immune modulation and had an average 150-fold increase in anti-AAV1 titer after exposure to AAV1.

Immune modulation using rituximab has become the therapy of choice for CRIM negative infants to maintain the efficacy of ERT (Elder 2013, Kazi 2017).

A similar mitigation of antibody response to AAV9 capsid and therapeutic protein has been observed in an expanded access trial of intravenous plus ICV administration of rAAV9-hASPA

Confidential Page 43 of 97

UMass Chan Medical School Clinical Study Protocol: AXO-GM2-001

Version 8.0, 09 June 2023

transgene in a child with Canavan disease (Corti et al. 2018). In this study with rituximab and sirolimus preconditioning, the immune response was abrogated.

In another ongoing trial, "Re-administration of Intramuscular AAV9 in Subjects with Late-Onset Pompe Disease," (NCT02240407, IND #17404) a similar immune modulation strategy to ablate B- and T-cells (rituximab, sirolimus, methylprednisolone and prednisone) prior to the initial exposure to AAV9 by intramuscular injection prevented the formation of antibody against AAV9 and the GAA transgene.

The ITI regimen was administered and well-tolerated in the two TSD subjects that are part of an ongoing Expanded Access clinical trial for AAVrh8-*HEXA/HEXB* gene therapy (IND# 18225).

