Schedule of Activities	Visit A	Visit B	Visit C	Visit D	Visit 1a	Visit 1b	Visit 2	Visit 3	Visit 4	Visit 5	Visit 6	Visit 7	Visit 8	Visit 9	Visit 10	Visit 11	Visit 12	Visit 13	Visit 14	Visit 15
	Week	Day -16	Day -7	Day	Day 1	Day 2	Day	Day 15	Day 22	Week	Week 6	Week 8	Week 10	Week 12	Week 16	Week 20	Week 24	Week	Week	Week
	- 8 ±28d	±5d	±3d	-2 ±1d	-	-	8 ±ld	±3d	±3d	4 ±3d	±4d	±5d	±4d	±7d	±7d	±7d	±7d	48 ±7d	72 ±7d	96 ±7d
Total hemolytic complement																				
(CH50) – AN due to platelet count decrease ⁴	X				AN	AN	AN	AN	AN	AN	AN	AN	AN	AN			AN	AN	AN	AN
Infectious disease testing -																				
As clinically indicated based on Medical History ⁵		AN																		
Research blood collection 7		X		X			X	X	X	X	X	X	X	X			X	X^{27}	X 27	X 27
Anti-AAVrh8 antibodies (ADA) ⁷		Х		X			X	Х	X	Х	X	Х	X	Х			X	X ²⁷	X ²⁷	X ²⁷
Transgene antibodies (ADA) ⁷		X		X			X	X	X	X	X	Х	X	X			X	X ²⁷	X ²⁷	X ²⁷
Neutralizing antibodies (Nabs) ⁷		X		X			X	X	X	X	X	X	X	X			X	X ²⁷	X ²⁷	X^{27}
GM2 ganglioside levels (serum) ⁷		X		X			X	X	X	X	X	Х	X	Х			X	X ²⁷	X ²⁷	X ²⁷
ELISpot		X		AN			X	X	X	X	X	X	X	X			X	X^{27}	X^{27}	X^{27}
Chest X-ray		X																		
Swallow Study ²⁵		X												X			X	X ²⁷		X ²⁷
ECG		X			AN		AN	AN	AN	AN	AN	AN	AN	X			AN	X ²⁷	AN	X ²⁷
EEG ⁸		X							X											
Echocardiogram 9		X																		
Pre-Surgical MRI 10 / CT			X																	
Intra-surgical CT scan					X															
Post-Surgical MRI					X															
MRI, MRS, DTI ¹¹	X													X			X	X^{27}	X ²⁷	
Surgical readiness determination		X																		
Central Venous Catheter placement 12		AN	AN	AN																
Rituximab infusion 13			X	AN																
Solu-Medrol infusion 14			X																	
Sirolimus 15			X	X	X	X	X	X	X	X	X	X	X	X	X	X	wean			
Prednisolone 16			X	X	X	X	X	X	X	X	X	X	X	X, taper	X, taper					

Confidential Page 55 of 97

Clinical Study Protocol: AXO-GM2-001

Version 8.0, 09 June 2023

Table 14: Schedule of Juvenile-Onset Participant Assessments (Continued)

Schedule of Activities	Visit A	Visit B	Visit C	Visit D	Visit 1a	Visit 1b	Visit 2	Visit 3	Visit 4	Visit 5	Visit 6	Visit 7	Visit 8	Visit 9	Visit 10	Visit 11	Visit 12	Visit 13	Visit 14	Visit 15
	Week - 8	Day -16	Day -7	Day -2	Day 1	Day 2	Day 8	Day 15	Day 22	Week 4	Week 6	Week 8	Week 10	Week 12	Week 16	Week 20	Week 24	Week 48	Week 72	Week 96
	±28d	±5d	±3d	±ld	-	-	±ld	±3d	±3d	±3d	±4d	±5d	±4d	±7d	±7d	±7d	±7d	±7d	±7d	±7d
Trimethoprim/sulfamethoxaz ole 17			X	X	X	X	X	X	X	X	X	Х	Х	X	X	X	Х			

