- 25. Participants must have a swallow evaluation test performed within 6 months prior to AXO-AAV-GM2 administration to assess the risk of aspiration. If aspiration risk is identified, it must be clinically managed prior to surgical procedures. Participants must have a swallow evaluation test performed at baseline and a clinical assessment of swallowing and a swallow study, if warranted, at Visit 9 (Week 12), Visit 12 (Week 24), Visit 13 (Week 48), Visit 15 (Week 96) and yearly thereafter for Years 3-5 (see Table 16).
- 26. BAER/VER/SSEP should be conducted without sedation or a prolongation of, or another episode of general anesthesia.
- 27. May be completed if visit occurs in person however not if the visit is completed as a tele-health
- 28. Tele-health will occur if Pt does not come to site in person

AN - As Needed

Confidential Page 57 of 97

Clinical Study Protocol: AXO-GM2-001

Version 8.0, 09 June 2023

Confidential Page 58 of 97

Clinical Study Protocol: AXO-GM2-001

Version 8.0, 09 June 2023

 Table 15:
 Schedule of Infantile-Onset Participant Assessments

Schedule of Activities	Visit A	Visit B	Visit C	Visit D	Visit 1a	Visit 1b	Visit 2	Visit 3	Visit 4	Visit 5	Visit 6	Visit 7	Visit 8	Visit 9	Visit 10	Visit 11	Visit 12	Visit 13
	Week - 8	Day -16	Day -7	Day -2	Day	Day	Day	Day	Day	Week	Week	Week	Week	Week	Week	Week	Week	Week
	±28d	±5d	±3d	-2 ±1d	-	2	8 ±1d	15 ±3d	22 ±3d	4 ±3d	6 ±4d	8 ±5d	10 ±4d	12 ±7d	16 ±7d	20 ±7d	24 ±7d	48 ±7d
ICF	X*	Х																
Inclusion/Exclusion Criteria	X*	Х																
Genetic Confirmation ¹	X*																	
Vital Signs 11	X*	Х	X	X	Х	X	X	X	X	X	X	X	X	X			X	X ²³
Weight	X*	X	X	X			X	X	X	X	X	X	X	X			X	X ²³
Height	X*	X	X											X			X	X ²³
Physical Examination	X*	X		X	X	X	X	X	X	X	X	X	X	X			X	X ²³
Neurologic Examination ¹²	X*			X		X	X	X	X	X	X	X	X	X			X	X ²³
Tele-health follow-up															X	X		X ²⁴
Tele-health Neuro Exam																		X ²⁴
Ophthalmology Exam			X															
HINE-2	X*									X				X			X	X ²³
BSID-III	X*									X				X			X	X ²³
Clinical Global Impression	X*									X				X			X	X
CBC with auto-differential ⁶	X				X	X	X	X	X	X	X	X	X	X			X	X ²³
Comprehensive metabolic panel ⁶	Х				Х	Х	X	Х	X	X	Х	Х	X	Х			X	X ²³
hsCRP	X				X	X	X	X	X	X	X	X	X	X			X	X ²³
GGT – AN due to elevated liver enzymes	AN				AN	AN	AN	AN	AN	AN	AN	AN	AN	AN			AN	AN
PT, PTT, INR, Blood Typing ⁶				X														
Total hemolytic complement (CH50) – AN due to platelet count decrease ⁶	AN				AN	AN	AN	AN	AN	AN	AN	AN	AN	AN			AN	AN

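### Tests for the four infections named in exclusion 13 depend on medical history, so a silent infection could go untested before immunosuppression and irreversible dosing

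*Combined protocol and SAP*

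**What the plan says.** Exclusion 13 in Section 9.2, repeated in the synopsis, bars "Current clinically significant infections including any requiring systemic treatment including but not limited to human immunodeficiency virus (HIV), Hepatitis A, B, or C".

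Each schedule has one infectious disease row, labelled "As clinically indicated based on Medical History", with one entry: AN at Visit B (Day -16). Table 14 footnote 5 (juveniles) and Table 15 footnote 10 (infants) carry the same rule: "Infectious disease testing will be performed as clinically indicated (i.e., based on Medical History) and will include HIV, hepatitis A, B and C", followed by five further agents.

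Section 13.4.4 gives a different panel of six agents. It includes hepatitis B, states no condition and no visit, and leaves out HIV, hepatitis A and hepatitis C.

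On timing, Section 8.2 says: "Starting on Day -7 of the study, the following will be initiated", and the list that follows includes rituximab, intravenous and oral steroids, and sirolimus. Section 8.3.2 adds: "The prophylactic ITI regimen will be administered starting 7 days prior to gene transfer and will continue to week 24". Section 8.2 then weans sirolimus up to Week 27. Dosing is on Days 1 and 2, and Section 9.3 notes that it cannot be withdrawn.

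**The concern.** An infection that nobody suspects is one that the history does not reveal. A test that only the history can prompt will miss it. Neither schedule has a medical history row; Section 9 mentions asking caregivers for the history at an optional virtual pre-screening visit.

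A child with a silent infection could thus follow the plan exactly and enter about 28 weeks of immunosuppression (7 days before Day 1 plus 27 weeks) and a one-time gene transfer with no specific test for an infection that the protocol itself names as a reason for exclusion. The Section 8.2 rule that stops the regimen for "intractable, severe opportunistic infections, not able to be managed with antibiotic, antifungal or antiviral therapy" acts only after exposure.

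**Working it through.** The plan states no figure to reproduce. The check sets the criterion beside the schedules and then looks at the timing.

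**1. Scheduled tests for the 4 named infections**

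| Agent in exclusion 13 | Table 14 | Table 15 | Section 13.4.4 |
|---|---|---|---|
| HIV | AN, Visit B | AN, Visit B | not listed |
| Hepatitis A | AN, Visit B | AN, Visit B | not listed |
| Hepatitis B | AN, Visit B | AN, Visit B | listed, no condition, no visit |
| Hepatitis C | AN, Visit B | AN, Visit B | not listed |

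Unconditional (X) entries are 0 of 4 in each table; history-driven entries are 4 of 4 in each. The footnotes list 9 agents and Section 13.4.4 lists 6, a difference of 3.

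**2. Unconditional screening that bears on infection**

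- Visit A, both tables: physical examination, CBC with differential, metabolic panel (which includes ALT, AST and bilirubin, Section 13.4.2), and CRP or hsCRP.
- Visit B, both tables: chest X-ray.
- Exclusion 15 has a liver limb, but it needs transaminases above 3 times ULN together with bilirubin above 2 times ULN. A raised ALT alone does not meet it.
- Exclusions 12, 16 and 18 rest on judgement. Exclusion 16 covers a contraindication to any study medication.

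These give the investigator results to weigh, but none is a specific test for the 4 agents.

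**3. The Section 8.2 rule as a backstop**

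The protocol adds: "Participants requiring discontinuation of the ITI regimen prior to Visit 1a (Day 1) will not be eligible for gene transfer". The regimen starts at Visit C (Day -7 ±3 days), so this bar can operate for 7 days nominally, range 4 to 10, and only if the infection becomes that severe in that time.

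**4. Room for a scheduled test**

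Visit windows from Tables 14 and 15:

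- Visit A, Week -8 ±28 days: Day -84 to -28.
- Visit B, Day -16 ±5 days: Day -21 to -11.
- Visit C, Day -7 ±3 days: Day -10 to -4.

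Time from sample to first rituximab:

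- From Visit A: 56 − 7 = 49 days nominal; minimum 28 − 10 = 18; maximum 84 − 4 = 80.
- From Visit B: 16 − 7 = 9 days nominal; minimum 11 − 10 = 1; maximum 21 − 4 = 17.

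Blood assays already scheduled as X are 4 at Visit A (CBC, metabolic panel, CRP, and CH50 in Table 14 or serum HexA in Table 15) and 6 at Visit B (CD19/20, capsid antibodies, transgene antibodies, neutralizing antibodies, serum GM2, ELISpot). Visit A has more time and fewer competing assays.

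**The case against.** The strongest reply is that this is a deliberate choice. Exclusion 13 is about current, clinically significant infection and requires no serology. Both tables state the history rule in the row and again in a footnote. That stands: a reader might infer that the schedules contradict the criterion, and they do not.

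A reader might also contrast exclusions 2 and 10, whose tests (swallow study; ECG and echocardiogram) are X at Visit B. The contrast proves little, because those criteria name their tests and exclusion 13 names none.

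A third tempting reading is that the investigator would have no result at all to weigh. The screening in step 2 of the working rules that out, and known or symptomatic infection would probably be found. Section 13.4.4 could even be read as routine hepatitis B serology. However, with no visit attached and both schedules saying AN, it cannot be relied on.

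Nor can undetected hepatitis alone set off the rescue steroids: Section 8.2.1 also requires two successive positive ELISPOT assays to capsid or transgene peptides.

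Finally, a Visit A result would be 18 to 80 days old at rituximab, and history would still have to cover that interval. This is a real limit, but a dated result plus history is more than history alone.

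**Conclusion.** The point holds as a cheap safety improvement; it does not correct an error. For a child with no suggestive history, 0 of the 4 infections named in exclusion 13 have an unconditional scheduled test before Day -7, in either table. The gap is confined to silent infection.

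Its size in children cannot be given. Prevalence is not in the documents and is not assumed. Stage 2 plans up to 10 infantile-onset participants, and the number of the 12 Stage 1 children already dosed is not stated. A reader might take the short period before Day 1 as a measure of risk; it describes only when the Section 8.2 bar can act.

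The conclusion assumes that the schedules govern over Section 13.4.4. The risks of the immunosuppression are deferred to the Investigator's Brochure (Section 8.7), which was not available, so further infection guidance there cannot be excluded.

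**What to change.** - In Table 15, change AN to a scheduled X for HIV and hepatitis A, B and C, and reword footnote 10 to match. Make the same change in Table 14 (footnote 5) only if undosed juveniles remain: Stage 2 is infantile-only, and the High-Dose rows of Table 10 list infants only.
- Draw the sample with the existing Visit A blood, within the limit of less than 10 mL per week (Table 14 footnote 7, Table 15 footnote 9).
- Require the results to be reviewed against exclusions 13 and 16 before the first rituximab dose. Repeat at Visit B only for new exposure or symptoms; since Visit B can fall 1 day before Visit C, rituximab would wait for that result.
- Specify assays suited to the participants' age: 6 to 20 months for Stage 1 infants, and 2 to 12 years for any remaining juveniles.
- Leave the other five agents as clinically indicated. The change covers the four that the protocol itself singles out.
- Add HIV, hepatitis A and hepatitis C to Section 13.4.4 and give it the same visit and conditions as the schedules.

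The cost is an amendment to one row and one footnote per table affected, a short edit to Section 13.4.4, a small extra blood volume, and occasional false-positive follow-up that could delay dosing in a rapidly progressing disease.
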